### 2.3 Fructose Alters Energy Homoeostasis and Causes Hyperuricemia

[figure not shown]
In support of our hypothesis that ATP depletion underlies liver injury in patients with NAFLD, our group has demonstrated that patients with biopsy-proven NAFLD have increased hepatic mRNA expression of KHK compared to matched controls (17). Indeed, in human pilot studies, intravenous (IV) fructose administration is associated with hepatic ATP depletion (20, 21) which can be assessed by  $^{31}\text{P}$  magnetic resonance spectroscopy (MRS) (22). Reduced hepatic ATP stores are more prevalent in overweight and obese subjects than in lean subjects (23). Furthermore, recovery from fructose-induced ATP depletion was found to be delayed in patients with NAFLD ( $n=8$ ) (24). However, a limitation to this existing work is the small sample size and the inability to assess a cause-effect relationship(s) between BMI, NAFLD, energy homeostasis, and histologic features of liver injury. In liver cells, ATP depletion could perpetuate chronic liver injury by making fatty hepatocytes less proliferative. Hepatic ATP depletion also encourages the expansion of liver progenitor populations (25), causes arrest in protein synthesis, induces inflammatory and prooxidative changes (26, 27), increases endoplasmic reticulum stress, promotes activation of stress-related kinases, induces mitochondrial dysfunction, and increases

apoptotic activity (28-30). This supporting data suggests that fructose may be associated with NAFLD, NASH, and progressive fibrosis. Further, a study by Loguercio *et al.* demonstrated that increased uric acid levels above the basal level after IV fructose infusion was significantly higher ( $p < 0.01$ ) in patients with cirrhosis (3 mg/dl) and NASH (1.9 mg/dl) than in healthy controls (1.2 mg/dl) (31). This effect was completely reversed by fructose 1,6-diphosphate which could replenish the ability to resynthesize ATP from ADP. Therefore, an IV fructose challenge could effectively differentiate healthy subjects, from chronic hepatitis, from cirrhosis (31).

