## 2.5 Use of MRI/ MRS as a Non-invasive Biomarker of NAFLD

Various MRI/MRS methods are used to investigate liver status (42-45). Tools used in this study will be extensions of these methods validated in other organs, and that we have adapted for use in the torso. All spectroscopy tools will use localized techniques, to provide volumetric hepatic metabolite measures. Hepatic energy homeostasis (ATP values) will be measured using an ultra-short TE sequence with “echo times” as short as 70  $\mu$ s, which increases the signal to noise ratio allowing shorter temporal sampling if needed. Hepatic lipid and water signals will be measured within a breath hold using  $^1\text{H}$  MRI sequences .

We will adapt the MRS acquisitions to provide a known reference against which to calibrate hepatic metabolite values. By calibrating the metabolites values, we will know exactly which metabolite(s) change and by how much, both within our cohort and in response to our dietary intervention study.

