### 3.6 Outcome measures

#### *Acute Fructose Challenge and MR Biomarkers*

**Primary:** The difference(s) in rate and extent of the dynamic changes in metabolism and energy and water homeostasis in patients with biopsy-proven NAFLD. Liver histology will be the primary predictor of disease and the primary outcome variable to which secondary measures (i.e. MR-biomarkers, metabolic parameters etc) will be measured.

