## 10. Statistical design and analysis

Coefficients of variance (CV) will be used to evaluate reproducibility of MRS/MRI baseline measures. Intra-class correlations (ICC) will be used to measure absolute test-retest baseline measure reliability for the test-retest subjects. ICCs will be calculated with a model that separates subject, voxel, measurement and error variances using an analysis of variance (ANOVA) method. We will include a number of multi-factorial random effects models (66, 67) which use a restricted maximum likelihood (REML) algorithm to prevent negative variance terms. The ANOVA model for metabolite estimates across all subjects will be  $M_{ijk} = \mu + S_i + V_{ij} + N_k + e_{ijk}$  where  $\mu$  is the average across all voxels,  $S_i$  = subject,  $V_{ij}$  = voxel and  $N_k$  = scan random effects, respectively and  $e_{ijk}$  is residual error. For ICC in individual subjects, we leave out the  $S_i$  term. ICCs for test-retest measures will be based on random-effects analysis of the variance models and will be computed as follows:  $ICC = \sigma^2_B / (\sigma^2_B + \sigma^2_w + \sigma^2_e)$  where  $\sigma^2_B$  is generalized between-subject variance of metabolites,  $\sigma^2_w$  is within-subject variance between scans 1 and 2 and  $\sigma^2_e$  is variance due to random noise (68). CVs for test-retest reproducibility will be calculated using  $CV = \sqrt{\sigma^2_w + \sigma^2_e} / \mu$ . Similarly we will obtain CVs from the first 20 subjects in Aim2 and will compare these to the normal population.

Dynamic changes will be characterized in a more *ad hoc* manner. From the metabolite estimates at time  $t$  ( $M_{ijkt}$ ), the following parameters will be measured for each individual (subscript  $i$ ): baseline ( $B_i$  = mean of  $M_{jkt}$ , where  $t$  = prior to fructose challenge), range of change from baseline ( $D_i = B_i - \min(M_{jkt})$  if any), time to maximal change ( $T_i$  = time to reach  $\min(M_{ijkt})$ ), time to baseline recovery ( $R_i$ , if applicable). A 95% confidence interval of baseline will be used to test if the metabolite level is recovered to the baseline. If it does not reach the baseline, we will estimate the baseline based on the assumption of a linear recovery rate. Since metabolite levels will be measured at discrete time points, spline smoothing will be used to fit the curve. These values will be averaged across the cohort of volunteers and simple measures of variance calculated.

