**10.1 Sample size and Statistical Power Consideration:** Assuming 20% change in hepatic ATP and uric acid (i.e. before~ Normal( $1.2, \sigma^2$ ) and after ~ Normal( $1, \sigma^2$ )), one-side test with alpha = 0.15, the power would be i) if  $\sigma^2 = 1$ , power = 0.523 ii) if  $\sigma^2 = 0.8$ , power = 0.629, iii) if  $\sigma^2 = 0.6$ , power = 0.784, iv) if  $\sigma^2 = 0.5$ , power = 0.875.

**10.2 Analytical and Statistical Approach:** We will test if the acute fructose challenge alters hepatic ATP in healthy volunteers compared to those with NAFLD and whether changes MR parameters and/or energy homeostasis can predict the histologic severity of NAFLD.

**10.3 Management of Missing data:** The occurrence of missing data in this trial is expected to be low. We estimate that careful selection of patients during the screening phase and the consent process should result in no more than 10% missing data from patients who drop out before completing the study.

**10.4 Justification of sample size:** A total of 67 patients will be included to compare the efficacy of acute fructose challenge on the metabolic and energy homeostasis changes in patients with NAFLD.

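### Recovery time R_i is judged against each subject's own baseline confidence interval, so it shifts with spectral noise and the number of baseline spectra, not only with ATP

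*Combined protocol and SAP*

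**What the plan says.** Section 10 reduces each subject's dynamic curve to four quantities: baseline B_i (the mean of the pre-fructose estimates), extent of fall D_i, time to maximal change T_i, and time to baseline recovery R_i. For R_i the rule is "A 95% confidence interval of baseline will be used to test if the metabolite level is recovered to the baseline". For subjects who do not recover, "If it does not reach the baseline, we will estimate the baseline based on the assumption of a linear recovery rate". On curve fitting: "Since metabolite levels will be measured at discrete time points, spline smoothing will be used to fit the curve".

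The plan gives no formula for the interval and no smoothing parameter. Appendix A says that several baseline spectra are acquired but not how many. Noise is to be estimated during the study: "Similarly we will obtain CVs from the first 20 subjects in Aim2 and will compare these to the normal population".

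The primary outcome in section 3.6 is the "rate and extent of the dynamic changes in metabolism and energy and water homeostasis" in patients with NAFLD. R_i is the only recovery-time parameter defined, and section 2.3 reports from a small pilot study that "recovery from fructose-induced ATP depletion was found to be delayed in patients with NAFLD".

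**The concern.** A recovery time should depend on how fast ATP returns. A confidence interval for a mean has a width set by measurement noise and by the number of measurements. If recovery means entering that interval, a subject with noisy spectra or few baselines meets an easier bar and appears to recover earlier, with no difference in physiology.

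The consequences differ in kind. Within any group, R_i carries extra variation that has nothing to do with the liver. Between groups, a difference in noise or baseline count would turn into a difference in R_i. Noisier spectra in NAFLD would work against finding the delayed recovery that section 2.3 describes.

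The non-recovery rule adds a second problem. Baseline has already been measured, so it cannot literally need estimating. Read as a projected time to reach baseline, the rule aims at B_i, while observed times stop at the lower limit of the interval. Both kinds of time enter one R_i.

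**Working it through.** The plan states no figure for R_i, noise or baseline count, so there is none to reproduce.

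**Inputs from the documents.** Section 10.1: "Assuming 20% change in hepatic ATP and uric acid", written as 1.2 to 1, which is 16.7% of 1.2; both depths were tried. Section 5: one hour of spectra after fructose. Section 3.1: 30 volunteers and 70 patients.

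**Assumed.** Noise (CV) of 3, 5 or 10% per spectrum; m = 5, 10 or 20 baseline spectra; minimum at 10 minutes; exponential recovery with time constant 20 minutes (linear recovery complete at 60 minutes as an alternative).

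**Step 1: the bar.** As a fraction of baseline, the half-width is h = t(0.975, m−1) × CV / √m. For m = 5 and CV 5%, h = 2.776 × 0.05 / 2.236 = 0.062, so recovery is declared at 93.8% of baseline.

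**Step 2: R_i for one identical noise-free curve.** R = 10 + 20 × ln(0.20 / h).

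| CV | m | h | R_i (min) |
|---|---|---|---|
| 3% | 5 | 0.037 | 43.6 |
| 5% | 5 | 0.062 | 33.4 |
| 10% | 5 | 0.124 | 19.5 |
| 5% | 10 | 0.036 | 44.4 |
| 5% | 20 | 0.023 | 52.9 |

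With a 16.7% fall, the five rows give 40.0, 29.8, 15.9, 40.8 and 49.3 minutes. With linear recovery, CV 5% and m = 5, 10, 20 give 44.5, 51.1 and 54.1 minutes.

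**Step 3: noise added even when all subjects are scanned alike.** With m = 5, each subject's SD has 4 degrees of freedom. Its 95% range is √(0.484/4) = 0.35 to √(11.14/4) = 1.67 times the true SD. At a true CV of 5%, h then ranges from 0.022 to 0.104, and R_i for the same curve from 54.5 to 23.2 minutes.

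**Step 4: with the spline.** Using one simulated spectrum every 3 minutes and a smoothing spline, median R_i at CV 3% is 41, 48 and 55 minutes for m = 5, 10 and 20; at CV 5% it is 34.5, 40 and 43.5. Smoothing weakens the effect but does not remove it. A fixed threshold of 90% of B_i gives 25.5 to 26 minutes at CV 3% and 27.5 at CV 5% whatever m is. At CV 10% it gives 29.5 to 31.5, so a little noise dependence remains.

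**Step 5: simulated 30 v 70 trials.** These use a Wilcoxon test at two-sided 5%, which is an assumption because the plan names no test for R_i. With the same physiology in both groups, false positives for the rule as written were 32–80% across set-ups at noise 3 v 5%, 12–25% at 4 v 5%, 33–62% at 10 v 5 baselines, and 4–7% when noise and baselines were equal. A fixed threshold of 95% of B_i gave about 4–5%.

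**Step 6: the two targets.** Take m = 5 and CV 5%. A subject rising from 80% at 10 minutes to 93.8% at 60 minutes is recovered, with R_i = 60. One who falls just short has a linear rate of 13.8/50 = 0.276 points per minute and needs 6.2/0.276 ≈ 22 more minutes to reach B_i, so R_i ≈ 82. Near-identical curves differ by about 22 minutes.

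**The case against.** The strongest reply is that the interval's formula is not given. Section 10 estimates variance components across subjects, and an interval built from one pooled variance is a fair reading. It removes most of the noise bias: simulated false positives at noise 3 v 5% fall to about 5–8%. This stands, provided baseline counts are also equal, but the plan says neither. If a band for single values was meant, most of the dependence on m goes but the dependence on noise stays (34.5, 24.3 and 10.4 minutes at CV 3, 5 and 10%).

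Second, section 10 calls the dynamic summaries ad hoc and speaks of averaging them over volunteers; section 3.5 calls the study exploratory. No sentence states that R_i is compared between groups. However, section 3.1 carries the Aim 1 measurements into NAFLD patients, section 3.6 makes rate and extent primary, and section 10.2 compares volunteers with patients.

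Third, a reader might infer that the comparison is biased, or that a delay in NAFLD will be hidden. The documents do not support that. They report no noise difference, and Appendix A lists the same Slot 1 baseline block for both groups. The possibility is open: the plan itself compares CVs, volunteers serve to optimise the protocol, section 4.1 allows the encoding to change if data quality is poor, and section 2.5 says the sequence "increases the signal to noise ratio allowing shorter temporal sampling if needed". Nothing carries the CV check into R_i.

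Fourth, a reader might conclude that half-recovery time should replace R_i because it showed more power at equal noise. Part of that gain came from a different curve fit and test. Half-recovery also measures something else: when only late recovery was slowed, its power was 37% against 81% for the rule as written at 3% noise.

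**Conclusion.** The concern holds in a limited form. On the natural per-subject reading, R_i depends on scan noise and baseline count as well as on physiology. The direction follows from the interval formula. The sizes, about 44 to 20 minutes over noise of 3 to 10% and 33 to 53 minutes over 5 to 20 baselines, rest on the assumed noise, baseline count and curve shape.

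Extra variation in R_i arises in every case. Between-group bias is conditional on a difference in noise or baseline count that the documents neither show nor exclude, so the high false-positive rates illustrate what such a difference would do and do not predict this trial. The mismatch between observed and projected times needs no assumption about noise differences. The plan should be corrected before R_i is calculated; the design need not change.

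**What to change.** In section 10:

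1. Keep R_i as time to baseline recovery, defined as the first time after the minimum at which the fitted spline regains a threshold set in advance and the same for every subject: for example 95% of B_i, or a high fixed fraction of the subject's own depletion. An alternative is B_i minus a margin from one pooled within-subject variance, with the same number of baseline spectra in all subjects.
2. Replace the linear projection with right-censoring at the last spectrum time common to both groups, and compare groups with a censored-data method such as the log-rank test.
3. Count and report subjects whose depletion never crosses the threshold.
4. Report half-recovery, if wanted, only as a supporting measure of early recovery rate.
5. Reconcile the acquisition period so that the common period is defined: one hour in sections 5, 9.1 and 9.4; 4 and 24 hours in section 3.1; post-biopsy recovery spectra in Appendix A.

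The cost is wording and a little analysis code, with the same scans and subjects. Some subjects will be censored, and some shallow depletions will have no R_i. Power need not suffer. In simulations with equal noise, the common threshold against the rule as written gave 94 v 87% (3% noise) and 79 v 70% (5%) for a delay over the whole recovery, and 80 v 81% and 41 v 28% for a delay confined to late recovery. Those gains rest on the same assumptions as the sizes above.

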### 3.5 Type of trial

Single-center, phase 1 exploratory study to evaluate the acute (baseline and dynamic) changes in metabolic, energy homeostatic and MR biomarkers in volunteers and patients with biopsy-proven NAFLD measures following IV challenge and dietary fructose restriction.

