## Appendix A:

### **MRI/MRS Protocols for Assessment of Energy Homeostasis and MR Biomarkers for NAFLD**

In all cases no patient repositioning will need to occur between data acquisitions for different MR nuclei. Primary measures are indicated in blue and include  $^1\text{H}$  MRI/MRS for water and fat measures and  $^{31}\text{P}$  UTE MRS for fructose measures. In all cases, the multiple acquisitions acquired prior to the injection of fructose will serve as test-retest cases for confirming measurement variance in the presence of pathology. Interleaved measures for experimental hypotheses may be moved or removed in order to ensure sufficient primary measures within the allotted MR time slot.

Only MR Slot 1 and Slot 2 protocols shown below will be used on the healthy volunteers for Aim 1 in order to optimize these protocols. The full MR protocol shown below will be performed for NAFLD subjects.

MR Slot 1 (Time 0)	MR Slot 2 (Post biopsy)
<math>^1\text{H}</math> MRI - anatomical $^1\text{H}$ MRI/MRS – water/fat $^{31}\text{P}$ UTE MRS – fructose baseline (multiple acquire) Fructose injection $^{31}\text{P}$ UTE MRS – fructose dynamic (multiple acquire) $^1\text{H}$ EPSI – water/fat $^{31}\text{P}$ UTE MRS – fructose dynamic (multiple acquire)	<math>^1\text{H}</math> MRI - anatomical for biopsy localization $^{31}\text{P}$ UTE MRS – fructose recovery (multiple acquire) $^1\text{H}$ MRI/MRS – water/fat

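### When ATP has not recovered by the last spectrum, the plan assumes straight-line recovery without censoring, so recovery time R_i depends partly on the rule and can be undefined

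*Combined protocol and SAP*

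**What the plan says.** Section 10 reduces each participant's metabolite curve to four numbers: baseline B_i (the mean before fructose), maximal fall D_i, time to maximal change T_i, and recovery time R_i. R_i carries the qualifier 'if applicable', with no criterion for when it applies.

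The recovery criterion is: "A 95% confidence interval of baseline will be used to test if the metabolite level is recovered to the baseline". The next sentence covers participants who do not meet it: "If it does not reach the baseline, we will estimate the baseline based on the assumption of a linear recovery rate". Within the observed series, "spline smoothing will be used to fit the curve". The paragraph ends: "These values will be averaged across the cohort of volunteers and simple measures of variance calculated".

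The section gives no slope method, fitting window, target for the line, cap, rule for a flat or falling slope, or censoring. Section 10.3 on missing data deals only with dropout.

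**The concern.** Taken literally, the sentence re-estimates the baseline. That can hardly be meant. B_i is the measured pre-challenge mean, and Appendix A provides repeated baseline spectra: "the multiple acquisitions acquired prior to the injection of fructose will serve as test-retest cases". What remains unknown in someone who has not recovered is when recovery would occur. The workable reading is therefore that R_i is projected along a straight line and then handled like an observed time.

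The plan does not treat the observed curve as straight, since it fits a spline. Projecting linearly beyond the data adds an assumption that the trial cannot check.

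The projected values would not fall evenly. Section 2.3 cites a small study (n=8) in which ATP recovery was delayed in NAFLD, so non-recovery by the last spectrum should be more frequent in patients than in volunteers. Section 3.6 puts the rate of dynamic change in the primary outcome, and R_i is the only recovery parameter defined. If R_i is compared between groups, the rule acts mainly on one of them.

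**Working it through.** The plan states no figure for R_i, so there is none to reproduce. What follows illustrates the rule and does not estimate this trial's bias.

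**Inputs from the documents**
- Section 10.1: "Assuming 20% change in hepatic ATP and uric acid", written as means of 1.2 and 1.0. As a fall from baseline this is 0.2/1.2 = 16.7%.
- Sections 5, 9.1 and 9.4: spectra run for one hour after fructose.
- Section 10: recovery means return to the 95% confidence interval of baseline.

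**Assumed inputs** (not in the documents)
- Nadir at 10 minutes, last spectrum at 60 minutes after infusion, and, for the slope check, one spectrum every 5 minutes.
- Baseline interval half-width of 5% or 2% of baseline. The share of the fall to be regained is q = 1 − half-width/0.1667, which gives 0.70 or 0.88.
- The line runs from nadir to last spectrum and on to the interval's lower limit. Truth and line use the same target.

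**Exponential recovery, time constants 30 and 60 minutes**

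Share regained at 60 minutes: f = 1 − exp(−50/τ) = 0.811 (τ = 30) and 0.565 (τ = 60).
True R = 10 − τ·ln(1 − q). Values up to 60 minutes are observed and used as they are; otherwise the rule gives 10 + 50q/f.

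| Half-width | | τ = 30 | τ = 60 | Difference |
|---|---|---|---|---|
| 5% (q = 0.70) | True R | 46.1 | 82.2 | 36.1 |
| | Plan's rule | 46.1 (observed) | 10 + 35/0.565 = 71.9 | 25.8 (−29%) |
| 2% (q = 0.88) | True R | 73.6 | 137.2 | 63.6 |
| | Plan's rule | 10 + 44/0.811 = 64.2 | 10 + 44/0.565 = 87.8 | 23.6 (−63%) |

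With decelerating recovery the line arrives too early, more so in the slower group, and the difference shrinks.

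**Lagged (sigmoid) recovery, q = 0.70**

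Take a logistic curve F with assumed midpoint 70 minutes and scale 15 minutes, rescaled to zero at the nadir. F(10) = 0.018 and F(60) = 0.339, so the share regained at 60 minutes is (0.339 − 0.018)/(1 − 0.018) = 0.327.
- True R: F must reach 0.018 + 0.70 × 0.982 = 0.705, so R = 70 + 15·ln(0.705/0.295) = 83 minutes.
- Plan's rule: 10 + 35/0.327 = 117 minutes.

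Here the rule overestimates.

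**Flat or negative slopes**

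For a least-squares line on 11 spectra (10 to 60 minutes), the sum of squares of time is 2750, so SE(slope) = noise/√2750 = noise/52.4. The share of slopes at or below zero is Φ(−slope/SE).
- If a quarter of the fall is regained linearly by 60 minutes, slope = 0.1667 × 0.25/50 = 0.000833 per minute. At 5% noise SE = 0.000953 and Φ(−0.874) = 19%. At 3% and 10% noise it is 7% and 33%.
- For the two exponential curves it is 0.3% (τ = 30) and 2.5% (τ = 60) at 5% noise.

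Small positive slopes also cause trouble. In the quarter-regained case at 5% noise, the positive slopes give R_i with 5th, 50th and 95th percentiles of 71, 125 and 761 minutes, against a true 10 + 50 × 0.70/0.25 = 150. A plain mean would be driven by a few values.

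**When spectra are acquired**
- Sections 5, 9.1 and 9.4: one hour.
- Section 3.1: also 4 and 24 hours.
- Section 9.4: mentions late recovery measures and a second, limited MRI to locate the biopsy site, which not every patient has.
- Appendix A: a post-biopsy slot with phosphorus recovery spectra and no clock time, listed for volunteers too, although Section 9.1 limits volunteers to 60 minutes and gives them no biopsy.

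The censoring time cannot be fixed until these are reconciled.

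**The case against.** The best defence is that the harm is conditional. Section 3.5 describes an "exploratory study to evaluate the acute (baseline and dynamic) changes in metabolic, energy homeostatic and MR biomarkers", and Section 10 itself calls the dynamic summaries ad hoc. Averaging is stated for volunteers only. Section 10.2 says "We will test if the acute fructose challenge alters hepatic ATP in healthy volunteers compared to those with NAFLD" and names no R_i contrast. The words 'if applicable' might let analysts leave R_i blank. If later spectra are acquired, less extrapolation is needed, and with truly linear recovery and low noise the rule does little damage. All of this stands as a limit on the point. It does not remove it: 'if applicable' has no criterion, dropping non-recoverers would itself bias R_i downward, and the later scans conflict with the one-hour schedule.

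Three stronger readings are tempting, and the documents do not support them.
- A reader might infer that the plan replaces measured baselines. The literal words say so, but B_i is defined as the pre-challenge mean, so this is most likely a wording slip.
- A reader might infer that bias can go either way for the same exponential curve, because a line run to the baseline mean gives longer times. That sets a line to the mean against a truth defined by the interval limit. The interval is the plan's stated criterion, in the sentence just before the rule. With that target the exponential bias is downward; overestimation needs a different curve shape.
- A reader might infer that the primary NAFLD comparison is biased. No passage says that R_i will be used in it.

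**Conclusion.** The point holds in a conditional form. Section 10 prescribes straight-line recovery for participants not seen to recover, without censoring and without a rule for slopes at or below zero. If R_i is averaged or compared, part of the result comes from that rule, probably more in NAFLD than in volunteers.

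In the illustrations the true group difference falls by 29% or 63% under exponential recovery, while under lagged recovery an individual R_i is overestimated by about 41% (117/83 = 1.41). Undefined values are uncommon for the exponential curves at 5% noise and frequent only when little is regained by 60 minutes. These sizes rest on assumed curve shape, nadir, spacing, noise and a 60-minute last spectrum. The missing censoring rule rests on the text alone. The sentence should be changed; confidence in the practical effect is medium.

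**What to change.** Replace the sentence on linear recovery with:

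> B_i is the measured pre-infusion mean for every participant. Recovery is the first time the fitted spline re-enters the 95% CI of B_i. R_i is not extrapolated: if recovery has not occurred by the last 31P spectrum, R_i is right-censored at that time, and it is summarised and compared by methods for censored data. The number whose level never leaves the CI and the number not recovered are reported by group. Percent of the fall regained at 60 min, (M_i(60) − min)/D_i from the fitted curve, is reported for each participant whose level leaves the CI, and is used as the continuous recovery measure in the healthy–NAFLD comparison and in models of histologic severity.

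Reconcile Sections 3.1, 5, 9.1, 9.4 and Appendix A on when, and in whom, phosphorus spectra are acquired, so that the censoring time is known. Limit group comparisons to the window common to both groups.

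Percent regained stays within the data: the two exponential curves above give 81% and 57% at 60 minutes with no projection.

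The cost is analysis wording and one clarification, with no extra scans or participants. A mean recovery time is no longer reported, and a median may not be estimable if more than half of a group is censored. Percent regained at 60 minutes then carries the comparison.

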### 2.2 Fructose as a Risk Factor for NAFLD

Like obesity, NAFLD and NASH are closely linked to nutrition and the “Western diet” which is rich in saturated fats and refined sugars. Although fat consumption has remained relatively stable, the marked increase in dietary fructose consumption (more than doubling in the past 30 years alone) supports the role of fructose in NAFLD and the metabolic syndrome (4-6). Although the mechanism(s) for fructose-related liver injury is not yet well defined, fructose-related hepatic adenosine triphosphate (ATP) depletion may contribute to liver injury. Observations in animals suggest that fructose induces metabolic syndrome and NAFLD independent of energy intake (7, 8). One key difference in fructose metabolism (as opposed to glucose) relates to ATP depletion and the necessity of adenosine monophosphate (AMP) kinase to replenish ATP stores. As opposed to glucose, initial fructose metabolism involves phosphorylation of fructose to fructose-1-phosphate by fructokinase (ketohexokinase, KHK) using the substrate ATP. Unlike glucokinase, the phosphorylation of fructose by KHK is specific for fructose and not rate limited (9). Replenishment of ATP stores requires phosphorylation of AMP back to ATP via AMP kinase (which is inhibited in insulin resistance (common *in patients with NAFLD*) or conversion to uric acid via xanthine dehydrogenase resulting in hyperuricemia.

The high activity of KHK in phosphorylating fructose to fructose-1-phosphate in the liver, could result in hepatic ATP depletion (10) with habitual fructose consumption.

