### 11.2 Risk to Human Subjects

#### 11.2.1 *Intravenous Fructose Challenge*

Fructose has been recommended as an intravenous energy source during parenteral nutrition for patients with hepatic disease, uncontrolled diabetes mellitus, and in the postoperative state. Fructose is metabolised in the liver where it causes increased lactate formation, high-energy-phosphate depletion, increased uric-acid formation, and inhibition of protein synthesis. This results in increased concentrations of blood-lactate and serum-uric-acid. In hepatic disease fructose infusion may theoretically lead to lactic acidosis.

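### Section 10.1 gives uric acid the same assumed fall as ATP although the protocol expects a rise, and section 10 summarises every MRS metabolite response by its minimum

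*Combined protocol and SAP*

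**What the plan says.** **Power (section 10.1).** The calculation is introduced with "Assuming 20% change in hepatic ATP and uric acid". One pair of normal distributions serves both measures: mean 1.2 before the challenge and 1 after, with a common spread and a "one-side test with alpha = 0.15". Four values labelled σ² (1, 0.8, 0.6, 0.5) are paired with powers of 0.523, 0.629, 0.784 and 0.875. Section 10.4 gives 67 patients and section 10.3 allows for 10% missing data.

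**Response summaries (section 10).** For the MRS metabolite estimates over time, the "range of change from baseline" is D_i = B_i − min(M), where B_i is the pre-challenge mean. The time to maximal change, T_i, is the time at which the minimum is reached. No maximum, signed change or absolute change is defined.

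**Expected directions.** On uric acid, section 2.3 reports from a cited study that "increased uric acid levels above the basal level after IV fructose infusion was significantly higher" in cirrhosis (3 mg/dl) and NASH (1.9 mg/dl) than in healthy controls (1.2 mg/dl). Section 11.2.1 says of fructose metabolism: "This results in increased concentrations of blood-lactate and serum-uric-acid". On phosphorus metabolites, section 2.2 says "initial fructose metabolism involves phosphorylation of fructose to fructose-1-phosphate", with ATP as the substrate, and section 2.4 lists phosphomonoester and inorganic phosphate beside ATP as observable by ³¹P MRS.

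**Planned tests (section 10.2).** Only hepatic ATP is named. No test, summary or direction is given for uric acid.

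**The concern.** A one-sided test is informative only if it points the right way. Section 10.1 points it downwards for a measure that the protocol's own background says goes up. By the mechanism described under Figure 1, uric acid is formed from AMP that is not recycled to ATP, so ATP and uric acid should move in opposite directions.

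The response formulas raise a related but separate problem. Section 3.6 makes the rate and extent of dynamic changes in metabolism and in energy and water homeostasis the primary outcome, and section 9.4 plans dynamic measures of ATP and of other metabolites. D_i and T_i are the only stated summaries of extent and timing. Their labels suggest change in any direction, but their formulas record only a fall. If a metabolite rises, the summary carried into the comparison with histology would not describe its response. If the analyst then switched to the maximum after seeing the curves, that choice would be driven by the data.

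**Working it through.** **1. Reproduce the stated power.** Inputs from section 10.1: difference 1.2 − 1 = 0.2, one-sided alpha 0.15. The number per occasion is not printed. I infer 60, because 60/(1 − 0.10) = 66.7, which rounds up to the 67 of section 10.4.

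Use a two-sample t-test with 60 per occasion (118 df, critical value 1.041). The noncentrality is δ = 0.2/(s·√(2/60)) = 1.0954/s, and power is P(t′(118, δ) > 1.041). The printed figures are recovered if the values labelled σ² are used as SDs.

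| s | δ | Power computed | Power stated |
|---|---|---|---|
| 1 | 1.095 | 0.523 | 0.523 |
| 0.8 | 1.369 | 0.629 | 0.629 |
| 0.6 | 1.826 | 0.784 | 0.784 |
| 0.5 | 2.191 | 0.875 | 0.875 |

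Used as variances, they give 0.523, 0.574, 0.646 and 0.695, which do not match.

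**2. The same test when the measure rises by 0.2.** Replace δ by −δ and keep the rejection region for a fall.

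| Printed value | Used as SD | Used as variance |
|---|---|---|
| 1 | 0.0166 | 0.0166 |
| 0.8 | 0.0081 | 0.0120 |
| 0.6 | 0.0021 | 0.0072 |
| 0.5 | 0.0006 | 0.0049 |

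On either reading the chance of a significant result is far below the alpha of 0.15.

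**3. The test aimed at a rise.** By symmetry the power is again 0.523, 0.629, 0.784 and 0.875. The sign error therefore changes neither the stated power nor the sample size.

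**4. D_i and T_i for a rising MRS metabolite.** Write the curve as M(t) = B + A·g(t), where A > 0 is the size of the rise and g is its shape, between 0 and 1.

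- Without noise, B − min(M) = −A·min g(t). This is zero if the minimum is taken where the curve is at baseline. It is negative if every point used lies above baseline.
- With measurement noise e(t) held fixed, a larger A raises or leaves unchanged each value B + A·g(t) + e(t). The minimum therefore cannot decrease, and D_i cannot increase. D_i is zero or shrinks as the true rise grows, whatever the shape.
- T_i is the time of the lowest value. That tends to lie where g is small, such as the start of the rise or the end of recovery, or where noise happens to be lowest. It is not the time of the peak.

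For a fall (A < 0) the same formulas give the depth and time of the nadir, which is what is wanted for ATP. How large D_i is for a rising signal depends on curve shape and noise. The documents give neither, so I attach no figure to it.

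**5. Which measures are affected.** D_i and T_i are written for estimates indexed by voxel, scan and time, that is, for MRS series. Under sections 5 and 9.4 uric acid is drawn at time 0 and at about 1 hour, so it has one before/after change and no curve. Uric acid is touched only by section 10.1, and the MRS metabolites only by the formulas.

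**The case against.** The strongest reply is that no planned analysis is wrong. The one-sided test appears only in the power statement. Section 10.2 names hepatic ATP alone, and no analyst who had read sections 2.3 and 11.2.1 would look for a fall in uric acid. The power figures are also the same in either direction. All of this stands. A reader might infer that the trial will miss its expected uric acid response; the documents do not support that, because they specify no directional uric acid test.

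On the formulas, the reply is that ATP depletion is the first principal objective, and that baseline minus minimum, time to minimum and recovery are the natural description of a depletion curve. The text hedges with conditions such as the change existing at all, and calls the approach ad hoc. It is right that the minimum suits ATP. The hedges do not help a rising signal, however: they leave its response undefined or near zero and put nothing in its place.

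A reader might also infer that the protocol predicts a rise in phosphomonoester which the formula would lose. It does not say so. It says that fructose is phosphorylated at the expense of ATP and, elsewhere, that phosphomonoester is observable. A rise is a reasonable inference from the two, not a stated expectation.

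Finally, it would be wrong to say that D_i and T_i fail for uric acid. They do not apply to it.

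**Conclusion.** The point holds in two limited parts.

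1. The assumption in section 10.1 has the wrong direction for uric acid. Applied literally, the test would be significant with probability of about 0.017 to 0.0006 for a 0.2 rise, against the stated 0.523 to 0.875 for a 0.2 fall. This rests on an inferred 60 per occasion and on the printed σ² values used as SDs; as variances the range is 0.017 to 0.005. Correcting the direction leaves power and sample size unchanged. It is an error in a stated assumption and not in a planned test.

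2. Minimum-only definitions of extent and timing are right for ATP and wrong for any MRS metabolite that rises. There D_i is near zero or negative and does not grow with the response, and T_i is not the time of the response. This follows from the formula for any curve shape. Whether a measured metabolite will rise is an inference from sections 2.2 and 2.4.

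Both should be corrected before analysis. Neither undermines the ATP objective.

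**What to change.** **Section 10.1.** State the direction for each measure, a fall for hepatic ATP and a rise for uric acid, and say that the power figures apply to each in its own direction.

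**Section 10, MRS metabolites.** Keep the minimum for ATP. For every other MRS metabolite, state the expected direction in advance and define D_i as the signed extreme of the smoothed curve in that direction, which is the maximum where a rise is expected. Where the direction is unknown, use the largest absolute deviation from baseline, keep its sign, and test it two-sided. Define T_i as the time of the same extreme.

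**Uric acid.** Say that it is summarised by the signed difference between the roughly 1-hour sample and the time 0 sample.

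**Cost.** A few sentences, with no new data, visits or patients. The one statistical price falls on measures tested two-sided: at alpha 0.15 with 60 per occasion, power for a 0.2 change is 0.369, 0.472, 0.648 and 0.771 across the four printed spreads used as SDs. ATP and uric acid, with directions stated, do not pay it.
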